8.6. Non-Medication Therapies or Procedures

The WHO Drug, September 2020, B3 will be used to classify non-medication therapies by therapeutic class. Prior non-medication therapy is defined as any non-medication therapy taken before the date of the first dose of study treatment. Concomitant non-medication therapy is defined as any non-medication therapy taken on or after the date of the first dose of study treatment.

Non-medication procedure data will be listed but not summarized.

8.7. Extent of Exposure

Exposure data will be summarized by total dose administered (mg), total volume administerd (mL) and the number of interruptions (SC Infusion). Study drug administration data will be listed.

8.8. Treatment Compliance

Not Applicable.

9. Pharmacokinetics

Pharmacokinetic analyses will be performed using the PKS. Note that placebo are not required.

PK parameters will be calculated for ALXN1830 using noncompartmental methods with Phoenix® WinNonlin® (Certara USA Inc., Princeton, New Jersey) Version 8.0 or higher. Calculations of individual PK parameters will be based on ALXN1830 concentrations and the actual sampling times elapsed from the actual reference dosing time data recorded during the study.

9.1. PK Sampling Schedule

Whole blood samples will be collected for measurement of serum concentrations of ALXN1830 as specified in the SoA (Protocol Section 1.3). All efforts should be made to obtain the PK samples at the exact nominal time relative to dosing within the specified window. Additional samples may be collected during the study.

9.2. Serum PK Endpoint

Following PK parameters will be derived from the serum ALXN1830 concentrations when feasible and supported by the available data.

For the single dose cohorts 1-2, PK parameters will be derived on Day 1.

For the multiple dose cohort 3, PK parameters will be derived on Days 1, 22, and 78.

For the multiple dose cohort 4 to 5, PK parameters will be derived on Days 1, and 22.

	Definition	
SD, MD	Maximum observed serum concentration	
SD, MD	Time to maximum observed serum concentration	
SD, MD	Area under the serum concentration versus time curve from time 0 to the	
	last quantifiable concentration	
MD	Area under the concentration-time curve during the dosing interval	
SD, MD	Area under the concentration-time curve from time 0 (dosing) to time	
	infinity	
MD	Concentration at predose times on Day 8, 15 and 22. Observed directly	
	from Data	
SD, MD	Terminal elimination half-life	
SD, MD	Terminal-phase elimination rate constant	
SD, MD	Total body clearance or apparent clearance	
SD, MD	Volume of distribution or apparent volume of distribution	
MD	Accumulation ratio	
	ED, MD	

Abbreviations: MD = Multiple-dose; SD = Single dose

Note: tau is the dosing interval for steady-state data, i.e., the time between doses (tau = 1 week).

The primary PK parameters will be summarized by overall treatment and the sub treatment category ADA status (at least one positive/negative). Boxplots will present PK parameters by ADA status and by healthy non-Japanese participants. Some PK parameters may not be calculated for all or some subjects, at the

discretion of the pharmacokineticist, if the concentration data are not deemed to be amenable to evaluation. Explanations for PK parameters that could not be estimated will be provided in the report.

Additional serum PK parameters may be calculated if deemed appropriate.

9.3. Presentation of Concentration Data

9.3.1. Handling of Missing Data

Missing concentration data for all participants who are administered scheduled study treatments will be considered as non-informative missing and will not be imputed. No concentration estimates will be provided for missing sample values.

For the derivation of AUC and for the individual serum concentration versus time curves, the following rules will apply:

- Concentration values below the assay's lower limit of quantification (BLQ) in pre-dose Day 1 samples will be treated as zero;
- The sampling time of pre-dose samples relative to dosing will also be treated as zero;
- BLQ's between two quantifiable samples will be set to missing;
- The first BLQ after the last measurable sample will be set to zero; any subsequent BLQ's will be set to zero;

For serum concentration summary the following rules will apply:

- All BLQ values will be set to zero;
- No further imputation will be applied to any missing values.

9.3.2. Listing and Presentation of Individual PK Data

The actual and nominal sampling times of PK blood sample collection will be listed for each participant and will include the deviation in time from the protocol scheduled time (i.e., nominal time), if applicable.

All measured concentrations will be presented in original precisions (i.e., significant figures) and units as reported by Bioanalytical lab – eg ng/mL.

Serum concentrations and time deviation data will be presented in a data listing by participant.

9.3.3. Summary of PK Concentrations by Matrix

Serum concentration data will be summarized separately by time point for each cohort/actual treatment using the following descriptive statistics: number of participants, arithmetic mean, SD, CV, geometric mean, geometric CV, median, minimum, and maximum.

Mean serum concentration versus scheduled time profiles will be presented in figures on both linear and semilogarithmic scales. Individual serum concentration versus nominal time profiles will be presented similarly.

9.4. Derivation of Pharmacokinetic Parameters

• The apparent C_{max} and the corresponding T_{max} will be read directly from the concentration-time plot (observed data).

AUCt will be calculated using the log-linear trapezoidal interpolation rule for extravascular model.

- The terminal elimination rate constant (λ_z) will be determined by log linear regression obtained on at least the 3 last quantifiable concentrations and will not include C_{max} ; $t_{1/2}$ is calculated by the program as $ln2/\lambda_z$;
- AUC_∞ will be calculated by the program as: AUC_∞ = AUC_t + AUC_{extrap} where last is the sampling time point of the last measurable concentration (tlast). AUC_{extrap} will be calculated by the program as: C_{last}/λ_z, where Clast is the observed concentration at time t_{last} and λ_z is the elimination rate constant during the apparent terminal elimination phase. AUC_∞ will only be presented for participants with a reliable λ_z;
- CL/F will be calculated by program as dose amount/AUC∞;
- V_z/F will be calculated by the program as (dose amount/AUC∞)/λ_z;

The following PK acceptance criteria will be applied to assess the reliability of elimination parameters:

- Number of points to calculate λ_z is greater than or equal to 3 excluding C_{max} point;
- The adjusted square of the correlation coefficient or coefficient of determination (R_{square} adjusted) for the goodness of fit of the regression line through the data points must be ≥0.80;
- AUC_{extrap} ≤20%.

Unreliable PK parameters will be listed but flagged and excluded from summary.

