c AUCSC = (Dose/CLIV) \* F, where CLIV is scaled as CLIV = (Median CLIV) × (body weight/median body weight)0.75. Median CLIV at 10 mg/kg = 239 mL/h with a median body weight of 82.7 kg (SYNT001-101); Median CLIV at 20mg/kg = 215 mL/h with a median body weight of 79 kg (SYNT001-104); Median CLIV at 30 mg/kg = 154 mL/h with a median body weight of 75.8 kg (SYNT001-101). Where median CLIV is not available at certain dose levels (eg 15 mg/kg), doses (mg/kg) are round up to obtain a conservative estimate. Median CLIV for 45 mg/kg is set to equal to median AUCIV at 30 mg/kg (2.03 mL/h/kg). The AUC represents AUC0-inf and AUCss for single and multiple doses respectively.

<sup>d Safety margin = (Monkey NOAEL in mg/kg) / (Human dose in mg/kg). Monkey NOAEL for weekly dosing is 100 mg/kg (Studies 2455-024 and 2455-016).

<sup>e Safety margin = (Monkey AUC0-120h at NOAEL) / (Predicted human AUCSC). Day 29 AUC0-120h =  $6420 \text{ h*}\mu\text{g/mL}$  at 100 mg/kg weekly SC (Study 2455-024).

f Safety margin = (Monkey AUC0-Tlast at NOAEL) / (Predicted human AUCSC). Day 92 AUC0-Tlast = 34800 h\*μg/mL at 100 mg/kg weekly IV (Study 2455-016).

<sup>g IgG reduction is based on predicted IgG reduction at equivalent IV dose in mg/kg. IgG reduction at median body weight is presented.

participant) or 24-fold (for a 75-kg participant) based on the NOAEL exposure from the 27-week IV monkey toxicity study. More importantly, a 30 mg/kg IV single dose has been tested in healthy participants and this starting dose of 1500 mg SC is expected to be roughly one-fifth to one-eighth of the exposure at 30 mg/kg IV, based on the low bioavailability observed in monkeys for ALXN1830 and in healthy participants from other anti-FcRn compounds. Based on these observations, the expected maximum IgG reduction at 1500 mg SC would be around -45% from baseline.

In the SAD portion, the SC dose will be escalated 1.5-fold from 1500 mg (Cohort 1) to 2250 mg (Cohort 2). An SRC review of safety, tolerability, and IgG data will be conducted before each dose escalation. Staggered dosing and pre-specified stopping rules based on safety and IgG reduction will be implemented in all cohorts.

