#### 9.4.2. Other Analyses

# 9.4.2.1. Pharmacokinetic Analyses

All PK analyses will be performed on the PK analysis set and will be reported by cohort and study drug within each cohort (ie, ALXN1830 or PBO).

The individual serum concentration data from participants who receive ALXN1830 SC with actual sampling dates and times will be used to derive the PK parameters by noncompartmental analysis methods using Phoenix WinNonlin 6.3 or higher. Pharmacokinetic parameter data will be presented in tabular form and descriptively summarized for all participants by cohort.

The following PK parameters will be derived as appropriate and data permitting:

Parameters	Dose Regimen	Definitions
C max	SD, MD	Maximum observed serum concentration
t max	SD, MD	Time to maximum observed serum concentration
[name]	Area under the concentration-time curve from time 0 to the last quantifiable concentration
AUC tau	MD	Area under the concentration-time curve during the dosing interval
AUC₀-∞	SD	Area under the concentration-time curve from time 0 (dosing) to time infinity
$t_{1/2}$	SD, MD	Terminal elimination half-life
$\lambda_{\rm z}$	SD, MD	Terminal-phase elimination rate constant
CL/F	SD	Total body clearance or apparent clearance
V d /F	SD	Volume of distribution or apparent volume of distribution
Rac	MD	Accumulation ratio

Abbreviations: MD = multiple-dose; SD = single-dose.

Additional details will be provided in the SAP.

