5.2. Secondary Endpoints

- Serum ALXN1830 concentration profiles and single- and multiple-dose PK parameters
- Change in serum IgG levels over time; FcRn saturation as measured by receptor occupancy
- Incidence of anti-drug antibodies and neutralizing antibodies to ALXN1830
- Quantitative assessment of safety, PK parameters, PD parameters, and immunogenicity between Japanese and non-Japanese healthy participants

6. Analysis Sets

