12.5. Physical Examination

A full physical examination will be performed at different timepoints as per the SoA (Section 1.3) in the Protocol. A symptom-driven physical examination of relevant body systems may be performed at other times, at the Investigator's discretion.

Physical examination data will be listed.

Interim Analyses

No interim analyses are planned.

13.

Controlled Document ID: **3903A.02**, Effective Date 31-Aug-2020 Filing requirements: TMF

14. Changes from Analysis Planned in Protocol

The study was terminated early, therefore cohort 2 has only 2 participants and cohort 6 has none. Therefore the secondary objective, to compare safety and tolerability, PK, PD, and immunogenicity of ALXN1830 SC between Japanese and non-Japanese healthy participants cannot be met and the secondary endpoint the quantitative assessment of safety, PK parameters, PD parameters, and immunogenicity between Japanese and non-Japanese healthy participants cannot be analyzed.

Analysis sets definitions as specified in Protocol Section 9.3 were updated as follows:

For the Enrolled Set participants also need to be randomized.

For the Pharmacokinetic Set participants need to receive at least 1 dose of study drug (only active) and have at least one post-dose serum ALXN1830 concentration measured. Participants will be analyzed according to the study drug they actually received. Serum concentrations will be summarized for all participants in the PKS. The exclusions from summary statistics for serum concentrations and/or PK parameters will be defined based on review of protocol deviations (if any) prior to database lock by PK scientist and study statistician at the discretion of the sponsor.

For the Pharmacodynamic Set participants need to receive at least 1 dose of study drug (active and placebo) and have evaluable serum Immunoglobulin data (IgG, IgG subtypes, Ig subtypes, CIC) or FcRn.

Immunogenicity Set was not define in the protocol, but added to the SAP as follows: The Immunogenicity Set (IGS) will include all participants who have a predose and at least 1 postdose ADA sample collected. Immunogenicity analyses will be performed using the IGS.

15. Reference List

FDA. Guidance for Industry, Clinical/Medical, Guidance for Industry: Immunogenicity assessment for therapeutic protein product. 2014.

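### SAP 9.4 gives only dose/AUC∞ for CL/F, but SAP 9.2 extends CL/F to multiple dosing, where that formula counts carry-over and understates clearance (minor; AUCtau is already planned)

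*SAP*

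**What the plan says.** **Protocol 9.4.2.1.** The parameter table marks AUC0-∞, CL/F ("Total body clearance or apparent clearance") and Vd/F for single dose only. AUCtau is marked for multiple dose.

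**SAP 9.2.** The corresponding rows are marked for both single and multiple dose. The days are set by two sentences: "For the multiple dose cohort 3, PK parameters will be derived on Days 1, 22, and 78", and "For the multiple dose cohort 4 to 5, PK parameters will be derived on Days 1, and 22". AUCtau is listed for multiple dose, with tau equal to 1 week.

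**SAP 9.4.** The only clearance formula is "CL/F will be calculated by program as dose amount/AUC", where the AUC is AUC∞. Vz/F is that quotient divided by λz. No clearance based on AUCtau is given. A reliability screen follows ("The following PK acceptance criteria will be applied to assess the reliability of elimination parameters"). It requires at least 3 points for λz, adjusted R² of at least 0.80 and AUCextrap of at most 20%. Values that fail are listed and flagged but left out of the summaries.

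**SAP 9.6 and 14.** These record departures from the protocol. Section 14 covers the Japanese comparison and the analysis sets ("Analysis sets definitions as specified in Protocol Section 9.3 were updated as follows"). Neither section mentions the extension of AUC∞, CL/F and Vd/F to multiple dose.

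**Protocol 4.3, Table 16, footnote c.** The sponsor's own dose/CL relation uses AUC0-inf and AUCss "for single and multiple doses respectively".

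**The concern.** Day 22 is the fourth weekly dose and Day 78 the twelfth. AUC from either day to infinity holds the tail of 3 or 11 earlier doses as well as the current one. Dividing a single dose by that area gives too small a clearance, and Vz/F inherits the error. The SAP thus widens the protocol's listing without the formula that multiple dosing needs and without recording the change.

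Multiple-dose PK is part of a secondary endpoint ("Serum ALXN1830 concentration profiles and single- and multiple-dose PK parameters"). On Day 1 there is no earlier dose, so dose/AUC∞ is appropriate there. Beside it, a Day 22 or Day 78 value on the same formula could suggest that clearance falls with repeated dosing when it does not. SAP 9.2 also summarises PK by antidrug-antibody status, and Cohort 3 runs 12 weeks partly to study immunogenicity, so a change in clearance over time is something readers will look for.

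**Working it through.** **1. The plan's own dose/CL relation.** Table 16 uses AUC = dose × F / CL, with CL = median CL × (weight/median weight)^0.75, F = 0.2 and weight 75 kg.
- 750 mg: 150,000 / [239 × (75/82.7)^0.75] = 675.3 (stated 675).
- 1500 mg: 300,000 / [215 × (75/79)^0.75] = 1450.8 (stated 1451).
- 2250 mg: 450,000 / [154 × (75/75.8)^0.75] = 2945.4 (stated 2948).

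The relation reproduces closely. For the weekly cohorts the protocol reads this AUC as AUCss, not as AUC to infinity.

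**2. Identity, with no model.** (dose/AUC∞) / (dose/AUCtau) = AUCtau/AUC∞ = 1 − share of AUC∞ after 168 h. The SAP formula is therefore always the lower of the two.

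**3. Size, linear one-exponential decline.** Let r = 2^(−7/h), with terminal half-life h in days. After dose n, (dose/AUC∞) / true CL/F = 1/(1 + r + … + r^(n−1)). The half-lives are assumed, because the documents give none.

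| h (days) | r | Error, dose 4 | Error, dose 12 |
|---|---|---|---|
| 1 | 0.0078 | −0.78% | −0.78% |
| 1.5 | 0.0394 | −3.94% | −3.94% |
| 2 | 0.0884 | −8.83% | −8.84% |
| 3 | 0.1984 | −19.72% | −19.84% |

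**4. Size with SC absorption.** In a one-compartment model with first-order absorption, let the faster of the two half-lives be 25% to 80% of the terminal one (assumed). After dose 4, dose/AUC∞ is low by 1.0-2.9% at 1 day, 11.4-22.0% at 2 days and 24.6-38.2% at 3 days. In the same settings dose/AUCtau is high by at most 0.66%.

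**5. Which half-life is plausible.** Footnote c gives median IV clearances of 154 to 239 mL/h. With an assumed volume of 3-6 L, half-life = 0.693 × V/CL runs from 0.693 × 3000/239 = 8.7 h to 0.693 × 6000/154 = 27 h. At 27 h the one-exponential error is 1.3%.

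**6. Whether the 20% limit catches it.**
- Cohorts 4-5 Day 22: samples run to Day 85, (85 − 22) × 24 = 1,512 h. Cohort 3 Day 78: samples run to Day 141, (141 − 78) × 24 = 1,512 h. Carry-over that is quantifiable is observed area. With one-exponential decline and h of 3 days or less, the area beyond 1,512 h is below 0.001%, so the limit does not flag the value.
- Cohort 3 Day 22: the next dose comes at (29 − 22) × 24 = 168 h. With one-exponential decline AUCextrap equals r, which reaches 20% at 7 × ln 2/ln 5 = 3.01 days. Below that, the value passes.
- Day 1 in Cohorts 3-5 also ends at 168 h. Applying the SC model of step 4 to the scheduled sampling times, Day 1 AUCextrap is 12-30% at 2 days and 28-61% at 3 days. Cohort 3 Day 22 is 26-48% at 3 days. Many of these values would be excluded from the summaries.

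**The case against.** **No sentence puts CL/F on Day 22 or 78.** That is so. It follows from the multiple-dose label together with the listed days, and the label could be met by Day 1 alone. SAP 9.2 also qualifies derivation by feasibility and leaves non-calculation to the pharmacokineticist. The symbol column of the SAP 9.2 table is not legible in the text available here, although the glossary has only CL/F and no steady-state clearance. This makes it an incomplete specification rather than proof of a wrong analysis. Discretion to omit a value does not supply the right formula, however.

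**The size may be trivial.** This stands. The only clearances in the documents point to an error of about 1-3% or less. One qualification is that IV clearance does not fix the terminal phase after SC dosing. With an assumed absorption half-life of 1.5 days, a 1-day elimination half-life gives −9.7%. Median IV clearance also falls across 10, 20 and 30 mg/kg (239, 215 and 154 mL/h), so kinetics may be nonlinear and every linear figure is then only indicative.

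**Stronger readings a reader might infer.**
- *Every multiple-dose participant would show a false fall in clearance from Day 1.* Step 6 does not support this. With SC absorption and a 3-day half-life, the Day 1 values are themselves screened out. A spurious fall would be visible mainly at half-lives up to about 2 days, or to about 3 days if decline is one-exponential.
- *A rise in clearance from antidrug antibodies would be hidden.* This is conditional on a long half-life. AUCtau and trough concentrations are unaffected, and SAP 11.1.2 overlays antibody category on individual PK plots.
- *The dose-proportionality model is distorted.* SAP 9.5 never names Day 22 AUCt, or any other specific parameter, as its input.

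**Conclusion.** The point holds as a minor one. If the single stated formula is followed on Day 22 or Day 78, CL/F and Vz/F are understated, under linear kinetics, by about the share of AUC∞ after 168 h. The direction is certain relative to dose/AUCtau. The size rests on an assumed half-life: negligible at 1 day and material from about 2 days. The AUCextrap limit gives no protection for Cohorts 4-5 on Day 22 or Cohort 3 on Day 78. The unrecorded departure from the protocol's single-dose listing stands whatever the half-life. Severity is limited because no hypotheses are tested, the summaries are descriptive, and the area needed for a correct clearance is already planned.

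**What to change.** In SAP 9.4, state that on Days 22 and 78 CL/F = dose/AUCtau and Vz/F = (dose/AUCtau)/λz, and that dose/AUC∞ applies only to the single-dose cohorts and to Day 1 of the multiple-dose cohorts. Alternatively, return AUC∞, CL/F and Vd/F to the protocol's single-dose listing. Whichever is kept, SAP 9.6 and 14 should record any difference from protocol 9.4.2.1.

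The cost is two or three sentences. No new samples are needed, because AUCtau and λz are already planned on these days. Dose/AUC∞ would no longer be reported for Days 22 and 78. Dose/AUCtau assumes steady state. After dose 4 it is within 0.7% at terminal half-lives up to 3 days in the settings above, but it would be about 7% high at a 7-day half-life with one-exponential decline, so the SAP should state that assumption.

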9.4.1. PK Parameters Summarization

Pharmacokinetic parameters derived from serum concentrations will be presented in data listings and summarized separately using the following descriptive statistics: number of participants, arithmetic mean, SD, arithmetic CV, geometric mean, geometric CV, median, minimum, and maximum.

9.5. Planned Statistical Models for PK Parameters and Concentrations

The primary analysis will be based on the PKS.

This document is confidential.

Controlled Document ID: **3903A.02**, Effective Date 31-Aug-2020 Filing requirements: TMF

Dose proportionality of Multiple-Dose (Cohort 3 to 5)

The power model will be used and will include the PK parameter as the response variable and dose (mg) as the explanatory variable. For this model, the variable dose will be treated as a continuous variable.

The form of the model is as follows:

PK Parameter = $e_{\alpha} \times Dose_{\beta} \times e_{\epsilon}$, where $Dose \ge 0$, and e_{ϵ} represents the associated error. Thus, perfect dose proportionality is met when β =1 (ignoring error). This becomes a linear relationship following a natural-log transformation, to which a linear regression will be fit by ordinary least squares (OLS):

In(PK Parameter) = α + β × In(Dose) + ϵ , where Dose > 0, α is the intecept, β is the slope and ϵ represents the associated error.

The estimate of β together with a 90% confidence interval (CI) will be provided (for each PK parameter model), and this will be used to quantify dose proportionality. According to Hummel et al. (2009), the following criterion may be used for exploratory dose proportionality evaluations: If the (two-sided) 90% CI for β is wholly contained within the interval, $[1+\ln(0.5)/\ln(\rho), 1+\ln(2)/\ln(\rho)]$, then dose proportionality is suggested across the investigated dose range. Here, ρ is defined as the ratio of the highest to lowest dose. This interval criterion will be reported along with the corresponding 90% CI estimate for β (presented to three decimal places).

 $ln(PK Parameter) = mu + \beta * ln(Dose)$

• *where β = 1 indicates perfect dose proportionality. Estimation of beta, along with its 90% CI, will be provided.

Assessment of Steady State (MAD)

For the MAD study portion, a visual assessment of C_{trough} concentrations will be undertaken. The geometric mean of C_{trough} values obtained from Days 8 through 22 will be plotted (y-axis) agains visit number (x-axis). The data points will be connected, and a box plot of individual values (for that visit) will juxtaposed to each geometric mean.

